The proposed PF-06293620 doses in the MAD portion were selected based on the preliminary PK/PD analysis and simulation from available data from the first 4 cohorts in the ongoing SAD study. Fixed dosages of 75, 150 and 250 mg Q4W were selected for this study to allow for adequate characterization of both the dose-response relationship for glycemic analytes (FPG, MMTT, mean daily glucose [MDG] and HbA1C), as well as to identify the maximum tolerated dose. Modeling suggests minimal accumulation ($R_{ac}=1.14$) of PF-06293620 after 3 dosages at 75 mg Q4W and approximately 1.4 and 1.6-fold increase in the exposure is predicted at 150 and 250 mg Q4W dosages, respectively. However, the predicted exposure at the highest dose (250 mg Q4W, ~3.1 mg/kg) is not expected to exceed the observed exposure at 6 mg/kg single-dose. The 6 mg/kg dose was found to be safe and well-tolerated. Guided by the dose-response relationship for baseline-adjusted FPG, the doses of 75 mg, 150 mg and 250 mg Q4W are deemed appropriate and adequate to allow for characterization of the dose-response relationship for PK, and PD changes. The 250 mg dose is expected to result in maximal fasting plasma glucose lowering. The 75 mg Q4W would approximately represent the dose for 50% maximal effect (ED50) and an intermediate dose of 150 mg Q4W was also proposed.

Proposed MAD doses, along with anticipated safety margins are listed in Table 4 below. The predicted human C_{max} and AUC_{tau} at the highest proposed dose would be approximately 122- and 20-fold below, respectively, the maximum observed exposures at 200 mg/kg (SC) in monkey in the pivotal, 3-month, toxicity study.

Table 4. Proposed PF-06293620 MAD Doses and Predicted Safety Margins based on the Exposures in Monkeys

Proposed PF-06293620 MAD Doses (mg)	Regimen	Predicted PF-06293620 Human Exposure		Projected Safety Margin*(fold)	
		C_{max} (μ g/mL)	AUC_{tau} (μ g*hr/mL)	C_{max}	AUC
75	Q4W	3.0	1471	653	126
150	Q4W	8.0	4486	245	41
250	Q4W	16.1	9448	122	20
TBD	TBD	--	--	--	--

Exposure at NOAEL doses (200 mg/kg) in monkeys:

IV: $C_{max} = 12,100 \mu$ g/mL; $AUC = 625,000 \mu$ g*hr/mL

SC: $C_{max} = 1,960 \mu$ g/mL; $AUC = 185,000 \mu$ g*hr/mL

*Margin calculated based on the NOAEL exposure/predicted human exposure

Source: Supportive Table 6 (RN909 Study B3501001: Preliminary PK report, May 2015)

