3. STUDY DESIGN

3.1. Study Overview

This is a randomized, placebo-controlled, double-blind (sponsor unblinded; subjects and Investigator blinded), single dose, and multiple-dose dose escalation study of PF-06293620. The study was originally to be conducted in approximately 6 planned single-dose cohorts. Based on the preliminary, unpublished, results from the first 4 SAD cohorts, the 1 mg/kg IV cohort will be evaluated but the 10 mg/kg IV cohort will not be conducted. Approximately 4 multiple dose cohorts are planned in an effort to seek a maximum tolerated dose (MTD) and evaluate different dosages for safety and tolerability. The multiple-dose cohorts will be initiated based on a review of the preliminary, unpublished safety and PK results from the first three SAD dose cohorts. The planned dosages, the route of administration, frequency of administration and the approximate number of subjects for the SAD cohorts are shown in [Table 5](#) and for the MAD cohorts in [Table 6](#) below.

Single-Dose Cohorts:

The SAD portion will be conducted in approximately 5 planned cohorts (a 6:2 ratio of active drug to placebo) with a total of up to approximately 40 subjects in an effort to seek a maximum tolerated dose (MTD). PF-06293620 will be administered subcutaneously(SC) at doses of 0.3, 1, 3, and 6 mg/kg. In addition, a 1 mg/kg dose, will be given intravenously (IV). The screening period will last up to 28 days and the treatment period will last approximately 84 days. Subjects will be required to be on stable, daily dosages of metformin. Subjects will receive a single dose of study treatment (PF-06293620 or placebo) on Day 1, with multiple PK and safety assessments during the confinement period in Clinical Research Unit (CRU) on study Days -1, 1, 2, 3 and 4 and will be discharged on Day 5. The subjects will return to the CRU for subsequent visits at which time safety assessments, including AE monitoring, clinical laboratory tests, vital signs, and ECG, as well as PK, MMTT, lipid and PD biomarker labs will be performed (See [Schedule of Activities](#)- SAD). In each SAD cohort, the first 2 subjects will be dosed with either PF-06293620 or placebo and observed for 24 hours. If no acute toxicity is observed in the first 24 hours, as defined in [Section 3.3.1](#), the remaining subjects in the cohort will proceed with dosing of either PF-06293620 or placebo. Dose escalation will not occur until all subjects in the cohort are enrolled and at least 6 subjects in

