The Schedule of Activities table in the study protocol provides an overview of the protocol visits and procedures. Refer to the Study Procedures and Assessments sections of the protocol for detailed information on each procedure and assessment required for compliance with the protocol.

Multiple-Dose Cohorts:

The multiple ascending dose (MAD) portion will be conducted in approximately 4 planned cohorts, 75 mg, 150 mg, 250 mg, and a fourth cohort with dosage and regimen to be determined based on the review of the safety data from the previous cohort(s), with a total of up to approximately 40 subjects (8 PF-06293620: 2 placebo per cohort).

Subjects and the site personnel in the MAD cohorts will be blinded to treatment and treatment regimen. The MAD cohorts will be run in parallel with the remaining SAD cohorts. Based on the ongoing review of the safety data of the previous SAD and MAD cohort(s) the order of initiation of the MAD cohorts may be adjusted but at no time will the dose exceed the PK exposure from the SAD portion. MAD safety data from the previous cohort(s) will be used to determine the dose and dose regimen of the fourth planned cohort. An additional fifth cohort may be studied to obtain further safety and PK data, increasing the planned total number of subjects to approximately 50. At no time will the MAD dose exceed PK exposure from the SAD. The MAD subjects will receive SC administration of study drug (PF-06293620 or placebo) every 4 weeks (on study Days 1, 29 and 57) in 3 of the originally planned 75 mg, 150 mg and 250 mg cohorts. However, after 150 mg/kg dose cohort, it was determined that it would be unnecessary to study doses higher than 150 mg/kg. A decision was made to study 50 mg/kg dose and to expand 75 mg/kg dose cohort for additional pharmacodynamics evaluations. The final study dose cohorts and number of subjects randomized are outlined in [Table 2](#).

Table 2. Final MAD Cohorts and Dosage Levels

Dose	Route	Frequency	Number of Subjects
50mg Placebo	SC	Q4weeks	8
			2
75mg Placebo	SC	Q4 weeks	16
			4
150mg Placebo	SC	Q4weeks	8
			2

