SAD Cohorts: To assess the relationship between the PK parameters and dose, dose normalized AUC_{inf}, AUC_{last} and C_{max} will be plotted against dose (using a logarithmic scale), and will include individual subject values and the geometric means for each dose. Geometric means will have a different symbol than the individual values. The values will be dose normalized (to a 1 mg/kg dose) by dividing the individual values and raw geometric means by dose. A footnote will be added to the plots to indicate that geometric means are presented on the plot.

Absolute/Relative bioavailability will be estimated as the ratio of dose-normalized adjusted geometric means for SC and IV for AUC_{last} and AUC_{inf}.

MAD Cohorts: To assess the relationship between the PK parameters and dose, dose normalized AUC_τ and C_{max} on Days 1 and 57, and dose normalized C_{min} on Day 57, will be plotted against dose (using a logarithmic scale), and will include individual subject values and the geometric means for each dose. Geometric means will have a different symbol than the individual values. The values will be dose normalized (to a 1 mg/kg dose) by dividing the individual values and raw geometric means by dose. A footnote will be added to the plots to indicate that geometric means are presented on the plot.

Dose-normalized natural log transformed AUC (SAD): AUC_{inf} (data permitting) and AUC_{last} ; and $AUC\tau$ (MAD) will be analyzed using a mixed effect model with treatment as fixed effects and subject as a random effect using a one-way analysis of variance (ANOVA). Estimates of the adjusted mean differences (Test-Reference) and corresponding 90% confidence intervals will be obtained from the model. The adjusted mean differences and 90% confidence intervals for the differences will be exponentiated to provide estimates of the ratio of adjusted geometric means (Test/Reference) and 90% confidence intervals for the ratios. SC is the Test treatment, and the IV is the Reference treatment.

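### SAP 10.2.3.3 normalises the fixed-mg MAD exposures to 1 mg/kg by dividing by dose, so the plotted values would be per mg under a per-mg/kg label, too small by a factor of body weight

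*SAP*

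**What the plan says.** **Normalisation rule.** SAP 10.2.3.3 has one plotting paragraph for SAD and one for MAD. Both contain the same instruction: "The values will be dose normalized (to a 1 mg/kg dose) by dividing the individual values and raw geometric means by dose". The MAD paragraph applies it to AUCtau and Cmax on Days 1 and 57 and to Cmin on Day 57.

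**Dose units.** SAD doses are weight-based: "PF-06293620 will be administered subcutaneously(SC) at doses of 0.3, 1, 3, and 6 mg/kg" (protocol 3.1), plus 1 mg/kg IV. MAD doses are not: "Fixed dosages of 75, 150 and 250 mg Q4W were selected for this study" (protocol 1.3.3), and protocol Table 6 also lists mg. SAP Table 2 gives the final MAD cohorts as 50, 75 and 150 mg. The SAP Section 3 text directly above that table uses another unit for the same cohorts: "However, after 150 mg/kg dose cohort, it was determined that it would be unnecessary to study doses higher than 150 mg/kg", and then "A decision was made to study 50 mg/kg dose and to expand 75 mg/kg dose cohort for additional pharmacodynamics evaluations". That makes four mg/kg entries.

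**Parameter definitions.** Protocol 9.3.1 defines the dose-normalised MAD parameters as the parameter divided by dose, with no per-kg reference dose.

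**Model.** The last paragraph on this topic in SAP 10.2.3.3 names dose-normalised MAD AUCtau, beside SAD AUCinf and AUClast, in an ANOVA with SC as test and IV as reference. Protocol 9.3.2 has only AUCinf and AUClast in that model, and SAP Table 5 marks MAD AUCtau as descriptive only.

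**The concern.** A rule that divides by dose returns exposure per unit of whatever the dose is measured in. For SAD that unit is mg/kg and the label is right. For MAD it is mg, and the label borrowed from SAD is wrong. A programmer who took the Section 3 text at face value and divided by 50, 75 or 150 as mg/kg would produce the same numbers under the same wrong label.

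The SAP states that its analyses are meant for regulatory submissions or manuscripts, and PK is the secondary objective. A figure whose axis is wrong by nearly two orders of magnitude would mislead anyone who set it beside the SAD figure; Cmax appears in both. If per-mg MAD AUCtau also went into the model with the 1 mg/kg IV cohort as reference, the estimated SC/IV ratio itself would be wrong by the same factor, not only its label.

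**Working it through.** **1. The protocol's own conversion.** Protocol 1.3.3 equates 250 mg with about 3.1 mg/kg and does not state the weight used.
- Back-solving: 250 / 3.1 = 80.6 kg (250 / 3.15 = 79.4 to 250 / 3.05 = 82.0, allowing for rounding).
- N-weighted mean weight in protocol Table 1 (SAD subjects): (9×89 + 6×93 + 6×77 + 6×90 + 9×88) / 36 = 3153 / 36 = 87.6 kg, which gives 250 / 87.6 = 2.85 mg/kg.
- The Table 1 group means run from 77 to 93 kg, giving 3.25 to 2.69 mg/kg. That range contains 3.1, so the protocol's figure is plausible but cannot be reproduced exactly.

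**2. The error factor.** For a subject of weight W given D mg, the mg/kg dose is D / W. Then (AUC per mg/kg) / (AUC per mg) = [AUC / (D/W)] / [AUC / D] = W. The factor is therefore body weight in kg:

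| Basis | Factor |
|---|---|
| Protocol conversion | about 81 |
| SAD Table 1 weighted mean | about 88 |
| SAD Table 1 group means | 77 to 93 |
| Eligible individual (inclusion criterion 2) | above 50, up to 150 |

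**3. Illustration with the predicted AUCtau in protocol Table 4.** The table's AUC margins reproduce from its inputs (185000 / 1471 = 126, / 4486 = 41, / 9448 = 20), so the values are read correctly. The 250 mg row is kept because the prediction is given, although SAP Table 2 no longer lists that cohort.

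| Dose | AUCtau (µg·hr/mL) | Per mg (AUCtau / D) | Per mg/kg, W = 80.6 | Per mg/kg, W = 87.6 |
|---|---|---|---|---|
| 75 mg | 1471 | 19.6 | 1581 | 1718 |
| 150 mg | 4486 | 29.9 | 2410 | 2619 |
| 250 mg | 9448 | 37.8 | 3046 | 3310 |

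Following the rule plots the third column under a label that belongs to the fourth or fifth.

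**4. Pattern across doses.** Per mg: 19.6 : 29.9 : 37.8 = 1.00 : 1.52 : 1.93. Per mg/kg at a common weight the ratios are identical, because W cancels.

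**5. The IV-reference model.** The only IV cohort is SAD 1 mg/kg, with predicted AUCinf 7059 in protocol Table 3.
- Mixed units, 75 mg: 19.6 / 7059 = 0.3%.
- Common mg/kg scale: 1581 / 7059 = 22% or 1718 / 7059 = 24%.

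The Table 3 and Table 4 predictions come from different sources, so none of these ratios estimates bioavailability. What carries over is the gap between them, which equals W whatever the exposures are.

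**6. The Section 3 entries read literally.** 150 mg/kg would be 150 / 6 = 25 times the top SAD dose, and 150 × 87.6 = about 13.1 g per injection day. That cannot stand beside Table 2.

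**The case against.** **The SAP does not say which dose is the divisor.** If each subject's own mg/kg dose were used, the label would be right. This does not rescue the rule as written. It also divides cohort geometric means by dose, a fixed-dose cohort has one dose and that dose is in mg, and no weight conversion is given.

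**Dose-proportionality within MAD is intact.** A reader might infer that the assessment is spoiled. It is not: a common factor only moves the axis. Nor are these plots the only evidence on dose and exposure, because SAP Tables 5 and 8 also summarise un-normalised AUCtau, Cmax, Cmin and Cav, and CL/F, which protocol 9.3.1 defines as dose over AUCtau.

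**The exposure limit does not rest on these plots.** A reader might infer that the commitment to keep MAD within SAD exposure is undermined. That commitment operates during escalation, and protocol 1.3.3 argues it on un-normalised exposure.

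**The reach is limited.** The 1 mg/kg phrase stands only in the plotting paragraphs. The tabulated dose-normalised parameters follow the protocol definition, which carries no per-kg label. No combined SAD and MAD plot is planned, and values can be converted because weight is collected.

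**The Section 3 entries look like slips.** The same paragraph and Table 2 give mg, so it is not reasonable to infer that doses of 150 mg/kg were given.

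All but the first of these points stand. They limit the consequences without making the MAD instruction correct. The IV-reference model remains the one place where mixed units could change an estimate. Table 5 and the protocol suggest that MAD AUCtau was not meant to be there, but the SAP text names it, and SAP Section 2 says the SAP supersedes the protocol's statistical considerations.

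**Conclusion.** The MAD normalisation rule in SAP 10.2.3.3 is wrong as written. Followed literally, it yields per-mg values under a per-mg/kg label, too small by a factor equal to body weight: about 81 on the protocol's conversion or about 88 on the SAD mean. No MAD weights are given, so neither figure is established for the MAD subjects; the eligibility limits bound the individual factor at above 50 and up to 150.

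The plotted MAD values are not comparable with the SAD values as labelled, though they can be made so. The unchanged dose pattern assumes similar weights across MAD cohorts. If cohort means differed as much as the SAD groups did, the per-mg and per-mg/kg patterns could differ by up to 93 / 77 = 1.21. An SC/IV ratio for MAD AUCtau in mixed units would be wrong by the full factor, but only if that model is run as the SAP text states.

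**What to change.** 1. In the MAD paragraph of SAP 10.2.3.3, state normalisation to a 1 mg dose and print the units on the plots (for AUCtau, µg·hr/mL per mg).
2. If a comparison with SAD or IV is intended, normalise each subject's value by that subject's mg/kg dose (administered mg divided by baseline weight) before taking geometric means. SAP Table 3 already defines baseline weight for MAD.
3. Decide whether MAD AUCtau belongs in the IV-reference model, and bring the model paragraph, SAP Table 5 and protocol 9.3.2 into agreement. If it stays, item 2 is required.
4. Reconcile the four mg/kg entries in SAP Section 3 with SAP Table 2 and the protocol, after checking the dosing records.

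This costs SAP wording and, at most, one derived variable. No new data are needed.

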10.2.3.4. PK Concentrations

To assess the single dose PK profile of PF-06293620, PK concentrations will be listed, summarized and plotted for subjects in the PK analysis set (as defined in [Section 7](#)), where missing and BLQ values will be handled as detailed in [Section 10.2.3.1](#) above.

Presentations for PF-06293620 will include:

- A listing of all concentrations sorted by dose, subject ID, period (for SAD) or day (for MAD) and nominal time postdose. The listing of concentrations will include the actual sample collection times, and the time of dosing. Deviations from the nominal time will be given in a separate listing.
- A summary of concentrations by dose (and Day, for MAD), and nominal time postdose, where the set of statistics will include n, mean, median, standard deviation, coefficient of variation (cv), minimum, maximum and the number of concentrations above the lower limit of quantification.
- Median concentrations against nominal time postdose by dose (based on the summary of concentrations by dose and time postdose), with all doses presented on the same plot. Two plots will be generated, so that the concentrations can be presented on linear and logarithmic scales. For MAD separate plots will be generated for Day 1 and Day 57.
- Mean concentrations against nominal time postdose by dose (based on the summary of concentrations by dose and time postdose), with all doses presented on the same plot. Two plots will be generated, so that the concentrations can be presented on linear and logarithmic scales. For MAD separate plots will be generated for Day 1 and Day 57.

- Plots of individual concentrations against actual time postdose by treatment (separate plots for each dose, and for Days 1 and 57 of MAD). Two plots per dose and Day will be generated, so that the concentrations can be presented on linear and logarithmic scales.
- Plots of concentration against actual time postdose by subject (separate line for each dose for SAD, and for Days 1 and 57 of MAD). Two plots per subject will be generated, so that the concentrations can be presented on linear and logarithmic scales.

The range for the x-axes of these plots will be decided on review of the data, and will depend on how long PF-06293620 concentration is quantifiable in the matrix.

For summary statistics and median plots by sampling time, the nominal PK sampling time will be used. For individual subject plots by time, the actual PK sampling time will be used.

10.2.4. Pharmacodynamic Analyses

PD biomarker data will include fasting plasma glucose, fasting glucagon, fasting GLP-1, 24-hr glucose profile (finger-stick), mean daily glucose profile, HbA1c, fructosamine, 1,5-anhydroglucitol, and glucose, insulin, C-peptide, glucagon and GLP-1 AUC after mixed meal tolerance test (MMTT, 4 hr). The relationship between changes in the values of these biomarkers with the pharmacokinetics of PF-06293620 may be explored. Exploratory PK/PD modeling may be performed if visual examination of the data is suggestive of a relationship.

The change and percentage change from baseline for PD biomarkers over the period of the study will be tabulated by treatment. The mean change from baseline values over time per cohort will also be tabulated. Data will be presented in tabular and graphical format and summarized descriptively. Descriptive statistics on change from baseline in fasting plasma glucose, fasting glucagon, fasting GLP-1, 24-hr glucose profile (finger-stick), HbA1c, fructosamine, 1,5-anhydroglucitol, and glucose, insulin, C-peptide, glucagon and GLP-1 AUC after mixed meal tolerance test (MMTT, 4 hr), and lipid parameters will be provided separately for each treatment and the pooled placebo group. The mean change from baseline over time with active treatment may be compared to the mean change from baseline over time with pooled placebo treated subjects using MMRM analysis with treatment as fixed effect, subject as a random effect, and baseline value as covariate adopting unstructured covariance structure. Figures of absolute values, change from baseline, and percentage change from baseline over time may be produced if needed.

The relationship between changes in the values of these biomarkers with the pharmacokinetics of PF-06293620 will be explored. Exploratory PKPD modeling may be performed if visual examination of the data is suggestive of a relationship.

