9.6. Exploratory Analyses

Exploratory analyses will be conducted for SAD and MAD, respectively. The individual subject's change and percentage change from baseline for PD biomarkers over the period of the study will be tabulated by individual subject. The mean change from baseline values over time per dose group will also be tabulated. Data will be presented in tabular and/or graphical format and summarized descriptively. Placebo subjects will be pooled across all dose cohorts for the respective stages of the study, ie, SAD placebo subjects and MAD placebo subjects. To explore the treatment effect¹⁶, the mean change and percentage change from baseline over time with active treatment will be compared to the mean change and percent change from baseline over time with placebo treated subjects. Descriptive statistics on change and percentage change from baseline in fasting plasma glucose, post prandial glucose, insulin, C-peptide and glucagon AUC after mixed meal tolerance test (MMTT, 4 hr), 24-hr glucose profile (finger-stick), HbA1c, fructosamine, 1,5-anhydroglucitol; fasting

glucagon, total and active GLP-1 will be provided separately for each treatment and the pooled placebo group.

Exploratory PK/PD analyses may be conducted on relevant safety and PD endpoints as permitted by the data.

Data listings will be produced by study portion (SAD or MAD), subject, dose cohorts, visit date, and time.

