3. STUDY DESIGN

This is a randomized, placebo-controlled, double-blind (sponsor unblinded; subjects and investigator blinded), single dose, and multiple-dose dose escalation study of PF-06293620. The study was originally to be conducted in approximately 6 planned single-dose cohorts. Based on preliminary, unpublished, results from the first 4 SAD cohorts, the 1 mg/kg IV cohort will be evaluated but the 10 mg/kg IV cohort will not be conducted. Approximately 4 multiple dose cohorts are planned to seek a maximum tolerated dose (MTD) and evaluate different dosages for safety and tolerability. The multiple-dose cohorts will be initiated based on a review of the preliminary, unpublished safety and PK results from the first three SAD dose cohorts. The subjects, investigators, CRO and site personnel (except site personnel responsible for drug preparation) will be blinded to treatment assignments. The Sponsor’s clinical research team or designee (e.g. Medical Monitor) will be unblinded.

Single-Dose Cohorts:

The SAD portion will be conducted in approximately 5 planned cohorts with a total of up to approximately 40 subjects to seek a maximum tolerated dose (MTD). PF-06293620 will be administered subcutaneously(SC) at doses of 0.3, 1, 3, and 6 mg/kg. In addition, a 1 mg/kg

dose, will be given intravenously (IV). The screening period will last up to 28 days and the treatment period will last approximately 84 days. Progression to the next dose will occur if the last dose was well tolerated and after satisfactory review of the available safety data. The cohorts will be studied in a sequential ascending fashion with 15 day post-dose safety data from all of the subjects in the current cohort being reviewed by the Sponsor and Investigators prior to commencement of treatment in the next cohort. Subjects will be assigned to cohorts on the basis of their order of entry into the study. Within each cohort, approximately 8 subjects will be randomized to receive either PF-06293620 or placebo with a 3:1 ratio. The dosage and dose escalation scheme is shown in Table 1.

Table 1. Planned SAD Dosage Cohorts

Cohort	Dosage mg/kg	Route of Administration	Total n	Active	Placebo
1	0.3	SC	8	6	2
2	1	SC	8	6	2
3	3	SC	8	6	2
4	6	SC	8	6	2
5	1	IV	8	6	2

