8.4. Covariates

For all analyses of covariance, endpoints baseline measurements are to be used as a covariate. All other potential covariates may be introduced when appropriate.

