10.2. Statistical Analyses

Data will be summarized in a descriptive manner. MMRM analysis with treatment, visit, and visit by treatment as fixed effects, subject as a random effect, and baseline value as covariate adopting unstructured covariance structure may be performed as indicated.

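### The only PD comparison with placebo that the plan commits to is unadjusted for baseline; the baseline-adjusted model is optional and, in SAP 10.2.4, lacks visit terms

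*SAP*

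**What the plan says.** **Committed.** Protocol 9.6 pools placebo within the single-dose and the multiple-dose part separately and says that "the mean change and percentage change from baseline over time with active treatment will be compared to the mean change and percent change from baseline" on placebo. It names no adjustment. SAP 10.2.4 commits to descriptive statistics on change: results for the PD markers and "lipid parameters will be provided separately for each treatment and the pooled placebo group".

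**Optional.** The SAP's one between-group PD comparison is that the "mean change from baseline over time with active treatment may be compared to the mean change from baseline". The sentence continues "over time with pooled placebo treated subjects using MMRM analysis with treatment as fixed effect, subject as a random effect, and baseline value as covariate", so this comparison is baseline-adjusted, but it only *may* be done. It has no visit or visit-by-treatment term. The general model in SAP 10.2 has both, and is also optional: "baseline value as covariate adopting unstructured covariance structure may be performed as indicated". SAP 8.4 adds "For all analyses of covariance, endpoints baseline measurements are to be used as a covariate", which applies only if such an analysis is run.

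**Elsewhere.** For ambulatory blood pressure (SAP 10.2.2.5) the SAP commits to a repeated-measures model with treatment, visit and baseline.

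**Allocation.** In the single-dose part, "Subjects will be assigned to cohorts on the basis of their order of entry into the study". Cohorts run in sequence, each with 6 active and 2 placebo subjects planned.

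**The concern.** Change from baseline is correlated with baseline. If placebo starts higher than a dose group by chance, it is expected to fall further with no treatment at all, and a raw-change contrast then understates the drug's effect. Protocol Table 1 shows placebo starting higher than every active single-dose cohort.

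The sponsor's team is unblinded during the study (protocol 5.2, SAP 3). An optional model lets people who may already have seen PD results by arm decide whether the adjusted estimate is reported.

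PD results matter here. Protocol 1.3.1 says they are to inform dose selection in later studies, protocol 1.3.3 used them in dropping a planned cohort, and SAP 3 expanded the 75 mg cohort for further PD evaluation.

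**Working it through.** **1. Inputs.** Baseline HbA1c (mean ± SD) from protocol Table 1, data cut-off 19 May 2015. The group sizes sum to 9 + 6 + 6 + 6 + 9 = 36, which matches the 36 randomised subjects stated in protocol 1.3.2.

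**2. Gaps.** Gap = placebo mean (8.7 ± 1.0, N=9) minus cohort mean. SE = sqrt(SD₁²/n₁ + SD₂²/n₂), with Welch 95% intervals.

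| Cohort | N | HbA1c, % | Gap | SE | 95% CI |
|---|---|---|---|---|---|
| 0.3 mg/kg | 6 | 8.1 ± 0.9 | 0.6 | 0.50 | -0.48 to 1.68 |
| 1 mg/kg | 6 | 7.7 ± 0.6 | 1.0 | 0.41 | 0.11 to 1.89 |
| 3 mg/kg | 6 | 8.2 ± 0.5 | 0.5 | 0.39 | -0.35 to 1.35 |
| 6 mg/kg | 9 | 8.3 ± 0.7 | 0.4 | 0.41 | -0.47 to 1.27 |

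For 1 mg/kg: sqrt(1.0²/9 + 0.6²/6) = 0.414. The weighted active mean is (6×8.1 + 6×7.7 + 6×8.2 + 9×8.3)/27 = 8.1, a gap of 0.6. Only the largest of the four gaps has an interval excluding 0, and that interval makes no allowance for having been picked as the largest.

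**3. Bias of raw change.** If the groups are chance samples from one population, the expected bias is (1 − b) × gap, where b is the slope of follow-up on baseline. The documents do not give b; I assume 0.6 to 0.9.

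- Gap 1.0 (1 mg/kg): 0.1×1.0 to 0.4×1.0 = 0.10 to 0.40 points.
- Gaps 0.4 to 0.6 (other doses): from 0.1×0.4 = 0.04 to 0.4×0.6 = 0.24 points.
- Between doses, 1 and 6 mg/kg differ at baseline by 8.3 − 7.7 = 0.6, so their contrast can shift by 0.06 to 0.24 points.

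Because placebo starts higher, the bias against placebo understates glucose lowering.

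**4. Precision.** With equal variances at both times and correlation ρ (so that b = ρ), the variance of the adjusted contrast relative to raw change is [(1+ρ)/2] × [1 + (gap²/SSx)/(1/n₁+1/n₂)]. From Table 1, SSx = 8×1.0² + 5×0.9² + 5×0.6² + 5×0.5² + 8×0.7² = 19.0. At the 1.0 gap the penalty is 1 + (1/19.0)/(1/9+1/6) = 1 + 0.0526/0.278 = 1.19. For ρ = 0.6 to 0.9 the ratio is 0.80×1.19 to 0.95×1.19, or about 0.95 to 1.13. Adjustment there may gain or lose a little precision.

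**5. Concurrency.** In the single-dose part as planned, 8 of 10 placebo subjects come from other cohorts than the dose in question. In the final multiple-dose cohorts (SAP Table 2) it is 6 of 8 for 50 mg and for 150 mg. For 75 mg it is 4 of 8, if its 4 placebo subjects count as one group. No stated model has a cohort or period term.

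**6. Feasibility.** Fasting glucose in the multiple-dose part has 20 post-dose visits (Days 2, 3, 8, 15, 28, 29, 36, 43, 57, 58, 59, 64, 71, 78, 84, 85, 99, 113, 141, 169). An unstructured covariance then has 20×21/2 = 210 parameters for 40 subjects.

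**The case against.** The strongest reply is that the SAP's only between-group PD comparison is already baseline-adjusted and that the SAP declares that it supersedes the protocol's statistical text. This is right as far as it goes. A reader who stops at the words *change from baseline* might infer that the SAP plans an unadjusted comparison, and its full sentence does not support that. But the adjusted model is optional, the SAP does not mark it as replacing the protocol's comparison, and under either document the guaranteed output is unadjusted.

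Second, the regression-to-the-mean formula assumes chance differences. If cohorts filled in sequence differ systematically, each regresses toward its own mean, raw change may be nearly unbiased, and adjustment can itself introduce bias. This stands, and it is why the bias figures are conditional.

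Third, requiring an unstructured model at every visit could be unworkable (step 6). This also stands, and the fix has to allow for it.

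Fourth, the study tests no hypotheses and PD is an exploratory objective. Protocol 1.3.3 also says that the multiple-dose levels were guided by a baseline-adjusted glucose dose-response and not by a raw-change table alone. That limits the consequence to interpretation. It also shows that the sponsor regards baseline adjustment as sensible.

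**Conclusion.** The point holds in limited form, as a recommended SAP change. The committed PD comparison is unadjusted, while the better analysis, already described, is optional and incompletely specified in SAP 10.2.4. The possible understatement of HbA1c lowering is about 0.1 to 0.4 points at 1 mg/kg and 0.04 to 0.24 at the other single doses. It rests on chance imbalance and an assumed slope of 0.6 to 0.9.

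Several stronger readings are not supported:

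- That placebo is typically a full point higher: 1.0 is the largest of four gaps, and the gap against all active subjects is 0.6.
- That an effect could take the wrong sign: the documents give no true effect size to set the bias against.
- That adjustment buys precision: at the 1.0 gap the variance ratio is about 0.95 to 1.13. The case rests on bias.
- That the multiple-dose part, the IV cohort or fasting glucose is imbalanced: this Table 1 HbA1c snapshot covers none of them.
- That adjustment cures non-concurrent placebo: it does not remove period effects.

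**What to change.** In SAP 10.2.4:

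- Replace *may be compared* with *will be estimated*. Report least-squares mean differences from placebo with 90% confidence intervals by visit, at named key visits, from a model with treatment, visit, treatment-by-visit and baseline. Apply it to fasting glucose, HbA1c, fructosamine, 1,5-anhydroglucitol, daily glucose and the meal-test AUCs.
- Name a fallback for when the unstructured covariance cannot be estimated: a structured covariance or ANCOVA at each visit.
- State that placebo is pooled separately for the single-dose and multiple-dose parts, as in protocol 9.6.
- Keep raw and percentage change as description.

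The cost is SAP wording before database lock; no new data are needed. The model assumes a common linear baseline slope, and precision may fall slightly where imbalance is large. Period effects remain, so a sensitivity analysis for cohort or period would be a useful addition.
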